Procedures	Visit 1 Screening	Visit 2			Visit 3			Visit 4			Visit 5			Visit 6 Day 15 (± 5 Days) Follow-Up	Visit 7 Day 29 (± 7 Days) Follow-Up		
		PLACEBO			Randomisation Day 0 Scopolamine or Placebo			Day 4 (± 2 Days) Scopolamine or Placebo			Day 8 (± 2 Days) Scopolamine or Placebo						
		IV Infusion	IV Infusion	IV Infusion	Pre	During	Post	Pre	During	Post	Pre	During	Post				
Infusion administration		X				X			X			X					
Adverse Events		X	X	X	X	X	X	X	X	X	X	X	X	X	X		
Cannulation Site Check		X		X	X		X	X		X	X		X				
POMS (Optional)		X		X	X		X	X		X	X		X		X		
CANTAB ** (Optional)			X			X								X			
WAIS * (Optional)			X*			X*			X*			X*	X*	X*	X*		
NEO-PI-FFI * (Optional)			X*			X*			X*			X*	X*	X*	X*		
PRISE (Optional)			X			X			X			X					
Subjective Assessment															X		

Randomisation will only occur at Visit 3 after HDRS is demonstrated to be ≥ 8 and YMRS < 6 . These measures will be conducted pre-randomisation (and consequently also pre-infusion).

Pre-infusion vital signs should be taken post cannulation. Post-infusion vital signs within 15 minutes of infusion stopping and 50 to 90 minutes post-infusion.

Visit 6 and 7 can be conducted by telephone in limited circumstances if a participant has withdrawn or is unwilling/unable to attend clinic at the scheduled time.

* Can be undertaken at any of the marked visit

** These include Paired Associates Learning (PAL), Spatial recognition, Delayed Match to Sample, ID-ED Shift, motor screening and Eyes of the Mind tests.

***Only inclusion criterion 7 and exclusion criteria 21 and 22 are required to be met for randomisation at Visit 3 only

Δ Pregnancy test (serum pregnancy test and pregnancy urine dipstick), when required, for female participants only. Serum result confirmed prior to Visit 3.

◦ Blood tests for U&Es (Urine and Electrolytes), LFTs (Liver Function Tests) and TFTs (Thyroid Function Tests) should be confirmed within acceptable ranges in the previous 4 months of the Screening (Visit 1). Can be performed if required at Visit 1 or 2 (results must be confirmed as acceptable prior to infusion).

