8.4.4.1 Vital signs

Vital signs will be recorded for all participants and will include: blood pressure (BP), heart rate (HR) (beats per minute (bpm)), and respiratory rate (RR) (respirations per minute). These will be recorded at screening, Visit 2 and at Visits 3, 4 and 5. Patients will rest for 5 minutes before measurements are obtained. Vital signs will be recorded prior to infusions and post infusions. Prior to infusion vital signs should be obtained post cannulation.

For post infusion vital signs will be taken within 15 minutes post-infusion administration and fifty to 90 minutes post-infusion, resting HR and BP will be measured, with a requirement for a HR ≥ 50 bpm, and BP ≥ 90 mm Hg Systolic and ≥ 60 mm Hg diastolic prior to visit completion. Clinical support is present to support and advise research staff and participants in relation to the management or treatment strategies that are required if the participants HR is < 50 bpm

or > 100bpm or if participant is hypotensive (BP < 90/60). Clinical support includes ready access to resuscitation equipment and clinical expertise.

Where BP and / or HR are abnormal when measured post-infusion the participants respiratory rate will additionally be recorded, and this information will be provided to an on-site clinician.

All participants will be required to remain in the HRB-CRFG for a period of observation by trial staff for a minimum of 90 minutes post infusion. Participants should be asymptomatic of potential IMP related symptoms as well as having satisfactory vital signs before discharge post infusion.

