If a participant withdraws before completing the study, the reason for withdrawal must be documented in their medical notes. Participants who request to have no further infusions, will be invited to complete pre-infusion questionnaires for remaining treatment visits. Ideally, all participants who discontinue the study should comply with specified follow-up procedures (days 15 +/-5, days 29 +/-7) as detailed in this protocol (i.e. assessments via interview compromising psychometric instruments, discussion of adverse effects and medication and phlebotomy – Table 2, Section 8.3). If the participant is unable to attend for follow-up procedures, a telephone interview will be offered to attain relevant study data. The only exception to this requirement is when a participant withdraws consent for all study procedures. If a study participant withdraws consent after just receiving or during an infusion, monitoring for 50-90 minutes post infusion for bradycardia, hypotension, dizziness and sedation must occur, with the study specific Adverse Event Form completed.

If a participant withdraws due to an adverse event, the investigator will arrange for follow-up visits until the adverse event has resolved or stabilised.

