9.8.2 Prohibited medications

The following medications are contraindicated during the randomised treatment period as they may potentially alter the pharmacokinetics of Scopolamine and any participants newly prescribed these medications at randomisation visit will be excluded from the trial prior to any infusion being administered.

- Physostigmine
- Biperiden
- Procyclidine
- Tricyclic Antidepressants with significant anticholinergic properties (e.g. Amitriptyline and Nortriptyline) that are causing the participant to experience anticholinergic side effects (e.g. blurred vision, constipation, urinary retention, cognitive difficulties).

Participants prescribed any of the above agents during the trial will not receive any further intervention (infusions of Scopolamine or placebo), however will be followed up for the remainder of the trial with data collected included in intention-to-treat analyses if one infusion and one follow-up assessment have been completed.

Participants cannot participate in any other IMP studies while participating in this study (Visits 2-7).

10. Safety reporting

Adverse events will be captured for all study participants from the time of consent for the duration of their participation in the study i.e. from the time of consent to their final study visit. A full AE review at each study visit will ensure that a complete evaluation of the safety and tolerability of the IMP is conducted.

All participants will have their heart rate and blood pressure measured prior to infusion and post-infusion to measure haemodynamic changes, with normal results (see section 8.4.4.1) required post-infusion prior to the participant completing their visit (minimum 90 min monitoring period).

If the readings have not returned to normal within this required 90-minute monitoring period a further period of monitoring will be conducted. A treating investigator must assess and decide if medical intervention is required based on their clinical judgement. Additionally, the PRISE questionnaire (this is optional for participants) will be used where participants agree to document other adverse effects prior to participants completing their clinical visits 2, 3, 4, and 5 (see Section 8.5). All adverse events will be reported to the Sponsor on the AE case report.

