10.3 Reporting responsibilities of the investigator

10.3.1 Adverse events/serious adverse events

Any AE whose onset occurred between the time of informed consent and the last completed visit, observed by the investigator or reported by the participant, whether or not attributed to the study medication, will be recorded on the AE case report form. The Site Investigator or delegate will follow AE's and SAE's reported during the treatment period until resolved, considered stable, or completion of patient participation in the Scopolamine trial (i.e. final follow up Visit). Follow up information will be sought and submitted as it becomes available. All SAEs will be followed up until resolution or they are clearly determined to be due to a participant's stable or chronic condition or intercurrent illness(es).

The following information will be recorded in the adverse event form: Adverse event term, description, date of onset, outcome, date of resolution, seriousness, severity, assessment of relatedness to the study medication, and action taken with study drug. The Site Investigator is responsible for the assessment of severity (intensity) and causality/relatedness to IMP for all AEs and SAEs. A SAE should also be substantiated by a source document(s). Follow-up information should be provided as necessary.

AEs considered related to the study medication as judged by an investigator or the sponsor will be followed up until the event is considered stable. All related AEs that result in a participant's withdrawal from the study or are present post-infusion will be followed up until a satisfactory resolution occurs. Participants will continue to be monitored for AEs throughout the study period up to and including visit 7.

It will be left to the investigator's clinical judgment whether or not an AE is of sufficient severity to require the participant's removal from treatment. A participant may also voluntarily withdraw

from treatment due to what he or she perceives as an intolerable AE. If either of these occurs, the participant must undergo an end-of-study assessment and be given appropriate care under medical supervision until symptoms cease or the condition becomes stable. Any pregnancy occurring during the clinical study and the outcome of the pregnancy should be recorded and followed-up for congenital anomaly or birth defect.

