17.4.1.4 Risks and hazards secondary to IV Scopolamine infusion

AEs that have occurred have been transient in nature (<3 hours) and have included light headedness, sedation, a transiently reduced heart rate and blood pressure (requiring no intervention) and the recognised anticholinergic adverse effects of dry mouth and blurred vision (Drevets and Furey, 2010; Furey and Zarate, 2013).

Pulsed IV administration has not been associated to date with potential AEs noted with high oral dosages including delirium, (hypo)mania, psychosis or disorientation (Furey and Zarate, 2013).

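### Protocol 8.11 sets 50-90 minutes of monitoring after consent is withdrawn at an infusion, which conflicts with the 90-minute minimum for all participants in 8.4.4.1 and section 10 (minor)

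*Protocol*

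**What the plan says.** Three places in the protocol govern how long a participant is watched after an infusion.

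- **8.4.4.1 (Vital signs)** gives the general rule: "All participants will be required to remain in the HRB-CRFG for a period of observation by trial staff for a minimum of 90 minutes" after the infusion. It adds a condition on leaving: "Participants should be asymptomatic of potential IMP related symptoms as well as having satisfactory vital signs before discharge post infusion". It also sets limits that must be met before the visit ends: heart rate at least 50 bpm, systolic pressure at least 90 mm Hg and diastolic at least 60 mm Hg.
- **Section 10 (Safety reporting, opening paragraphs)** repeats the rule. Normal heart rate and blood pressure are "required post-infusion prior to the participant completing their visit (minimum 90 min monitoring period"). It then provides for an extension: "If the readings have not returned to normal within this required 90-minute monitoring period a further period of monitoring will be conducted".
- **8.11 (Discontinuation/withdrawal)** addresses consent withdrawn during an infusion or just after one. In that case "monitoring for 50-90 minutes post infusion for bradycardia, hypotension, dizziness and sedation must occur", and the study's adverse event form is completed.

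The range 50 to 90 minutes also appears in 8.3.4, 8.3.5, 8.4.4.1 and the notes to Table 2. There it is the time at which a reading is taken: "Post-infusion vital signs within 15 minutes of infusion stopping and 50 to 90 minutes post-infusion".

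**The concern.** A range that starts at 50 minutes and a floor of 90 minutes cannot both be the required monitoring period. Section 8.11 is where staff would look when someone withdraws consent at an infusion. Its instruction is specific and mandatory, so it could be followed in preference to the general rule. Staff who did so could stop at 50 minutes and find no condition on discharge and no extension in the sentence they were following.

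The stake is participant safety in one uncommon situation. The protocol's risk section (17.4.1.4) says "AEs that have occurred have been transient in nature (<3 hours) and have included light headedness, sedation", along with transient falls in heart rate and blood pressure that needed no intervention. Effects may therefore still be present at 50 minutes.

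There is also a small effect on data. SAP 14.1 plans a discussion of expected events over the 90 minutes after infusion, and Protocol 10.2.1.2 makes listed side effects reportable if monitoring has to run beyond 90 minutes. For a participant whose monitoring ended at 50 minutes, the SAP window would be cut short and that reporting trigger could not operate.

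**Working it through.** There is no statistical figure to reproduce. The check is a comparison of the texts with one subtraction.

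**Inputs**

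| Item | 8.11 | 8.4.4.1 and section 10 |
|---|---|---|
| Who is covered | Participants withdrawing consent during or just after an infusion | All participants |
| Monitoring time after infusion | 50 to 90 minutes | At least 90 minutes |
| Condition on discharge | None in the sentence | No symptoms, satisfactory vital signs |
| Extension if readings are abnormal | None in the sentence | Yes (section 10) |
| Effects to watch for | Bradycardia, hypotension, dizziness, sedation | Heart rate, blood pressure, drug-related symptoms |

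**Step 1: do the two times overlap?** Let t be the monitoring time in minutes. Section 8.11 is met when 50 ≤ t ≤ 90. The general rule is met when t ≥ 90. Both are met only at t = 90.

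**Step 2: size of the shortfall.** The largest shortfall allowed by 8.11 read alone is 90 − 50 = 40 minutes, which is 40/90 = 44% of the general minimum. The upper end of 90 also leaves no room for the extension in section 10.

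**Step 3: is 8.11 a stated exception?** The same part of 8.11 does mention an exception for someone who withdraws consent for all study procedures. That sentence follows the text on follow-up visits and the telephone interview, and it qualifies those. It does not concern observation after an infusion. Section 8.4.4.1 contains no carve-out either.

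**Step 4: where might 50-90 come from?** Everywhere else in the protocol where it appears, the range is the window for the second vital-sign reading. Reuse of that window as a duration is the likeliest explanation, but the documents do not say so. The explanation would not remove the conflict.

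**Step 5: which participants are left exposed?**

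- Section 8.7 asks participants whose infusions are not completed to complete everything else in the scheduled visits.
- Section 8.11, in its last paragraph, arranges follow-up visits after a withdrawal due to an adverse event until the event resolves or stabilises.
- Section 10.3.1 requires supervised care until symptoms cease or the condition is stable for someone who leaves treatment because of an intolerable adverse event. It also says that related events that lead to withdrawal "or are present post-infusion will be followed up until a satisfactory resolution occurs".

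The participant not caught by these provisions is mainly one who withdraws consent without an adverse event, at a site that reads 8.11 on its own.

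**The case against.** The strongest reply is that there is no real gap. Sections 8.4.4.1 and 10 both apply to all participants, and 8.11 does not disapply them. Staying 90 minutes satisfies every rule. Participants at most risk, those who stop because of symptoms, are covered by 8.7, 10.3.1 and the end of 8.11. Most of this stands, and it is why the point is minor. It does not remove the conflict, because a mandatory sentence in the protocol still names a period that starts below the protocol's own minimum.

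A second reply is that the shorter period may be deliberate. Section 8.11 lets participants withdraw at any time and without consequences, so someone who has withdrawn consent cannot simply be kept for 90 minutes. This is possible, but the text states no such purpose. If it was intended, 8.11 should say so and 8.4.4.1 should allow for it.

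Three stronger readings are tempting, and the documents support none of them.

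- A reader might infer that these participants have no discharge condition and no extension at all. That holds only if 8.11 is read in isolation.
- A reader might compare 50 and 90 minutes with the three hours in 17.4.1.4 and state what share of the effect period each covers. Three hours is an upper limit on reported durations, not a typical one, so such shares would mean little. They would not support 90 minutes in particular either.
- A reader might take the 6 participants whom Protocol 11.2 allows to be missing at Visit 6 as a cap on the number affected. That figure is a planning allowance for missing outcomes and does not bound consent withdrawals at an infusion.

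**Conclusion.** The inconsistency is real and the sentence in 8.11 is wrong as written. Followed literally, it allows monitoring to end up to 40 minutes before the minimum that the protocol sets for everyone, and it does not repeat the discharge conditions or the extension.

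The severity is minor. The general rules remain in force, and other sections cover stopped infusions and withdrawals due to adverse events. The remaining exposure is mainly a participant who withdraws consent without an adverse event. The documents give no frequency for this, so no number of cases can be stated. The primary endpoint, the sample size and the efficacy analyses are untouched. The effect on the narrative discussion in SAP 14.1 would be slight.

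The textual conflict rests on no assumption. The view that the reading window was carried over as a duration is an inference, and the conclusion does not depend on it.

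**What to change.** In the 8.11 sentence, replace the 50-90 minute phrase with: *monitoring for the section 8.4.4.1 observation period (minimum 90 minutes, with its discharge conditions, extended as in section 10 if readings are not normal) will be offered and carried out unless the participant declines to stay*. Keep the four listed effects and the adverse event form. The window of 50 to 90 minutes then serves only as the time of the second vital-sign reading. Recording a refusal to stay would be sensible but is optional, since resolving the conflict does not require it.

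If the sponsor did intend a shorter period after consent is withdrawn, the alternative is to say so in 8.11 and add the matching exception to 8.4.4.1 and section 10.

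The cost is one sentence. Staff time does not exceed what 8.4.4.1 already requires. Section 15.1 sends all protocol modifications for regulatory and ethics review, so the change should go into the next amendment and does not justify one of its own. If all infusions have already been given, which the documents do not establish, the change would have no practical effect.

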8.12 Outcome measures

8.12.1 Effectiveness Assessment

8.12.1.1 Primary outcome measure

The primary outcome measure will be the change from Visit 2 in severity of objective depressive symptoms after the final scheduled treatment as measured by change in the HDRS depression score from Visit 3 (pre-infusion and randomisation) to Visit 6.

8.12.1.2 Secondary outcome measure

1. Remission of depressive episode after the last IV treatment (measured objectively at Visit 6), and is defined as occurring when an individual has:
 - (i) a HDRS score ≤7
 - (ii) a MADRS score <6
2. Remission of depressive episode at follow-up (measured objectively at Visit 7)
 - (i) a HDRS score ≤7
 - (ii) a MADRS score <6
3. Response to a depressive episode after the last IV treatment (measured at Visit 6) is defined as:
 - (i) a 50% reduction in MADRS score at Visit 6 compared to Visit 3

4. Response to a depressive episode at follow-up (measured objectively at Visit 7)
 - (i) a 50% reduction in MADRS score at Visit 6 compared to Visit 3
5. Improvement in mood symptoms measured with the HDRS and MADRS at visits 5, 6 and 7 compared to Visit 3.
6. Improvement in objectively measured overall functioning, measured with the GAF at Visit 5, 6 and at follow-up at Visit 7 compared to Visit 3
7. Improvement in objectively rated illness severity, measured with the CGI-S at visits 4, 5, 6 and 7 compared to Visit 3 and CGI-I at visits 4, 5, 6 and 7 compared to Visit 3.
8. Changing subjective measured depressive symptoms with the POMS and VAS
 - (i) a reduction in POMS score post-infusion compared to pre-infusion at visits 2, 3, 4 and 5 across the six different factors of the POMS (tension, depression, anger, fatigue, vigour and confusion).
 - (ii) a reduction in VAS scores post-infusion compared to pre-infusion at visits 2, 3, 4 and 5 across 8 items (happy, restless, sad, anxious, anger, drowsiness and alertness).
9. A change in subjectively measured depressive symptoms at Visit 6 compared to Visit 3 as measured with the POMS and VAS.
10. A reduction in subjectively measured depressive symptoms at follow-up (Visit 7) compared to Visit 3 as measured with the POMS and VAS.
11. Psychiatric inpatient admission of a participant due to depressive episodes between Visit 2 and Visit 7.
12. Antidepressants medication use or change by a participant due to depressive episodes over the duration of the study (Visit 2 to Visit 7):
 - (i) Introduction of a new antidepressant (yes / no)
 - (ii) Increase in dose of an existing antidepressant (yes / no)
13. Change in motor processing, visual and spatial memory (3 categorical variables) at Visit 6 compared to Visit 2 based on the CANTAB battery of tests.
14. Occurrence of a hypo (manic) episodes at visits 3, 4, 5, 6 or 7, as defined by a score of >6 on the YMRS.
15. Occurrence of other adverse effects as observed on monitoring of vital signs, reported by participants or measured utilising the PRISE questionnaire

9. Treatment of Trial Participants

9.1 Description of study treatment(s)

Investigative Medicinal Product: (Active treatment): Scopolamine (Hyoscine Hydrobromide 600 micrograms/ml, 1 ml) Dosage = 4µg/kg in 100mls of Saline administered intravenously over 15 minutes via pulsed infusion. The Scopolamine dose is µg of drug per kg weight of the participant.

Scopolamine supplier: Martindale Pharmaceuticals, Essex, UK.

Placebo: Commercially available 0.9% sodium chloride 100ml infusion bag will be used as the placebo control in this trial. It will be administered intravenously over 15 minutes via pulsed infusion. The volume addition of active drug (hyoscine hydrobromide) will on average be less than 1ml (100kg patient or less) for each infusion bag, therefore no volume addition is required for the preparation of the placebo infusion bag as the volume difference to the active treatment infusion will be negligible to the total volume to be infused (100mls + volume overage in each bag) and will not be noticeable to personnel administering the infusion, thereby maintaining the blind.

Placebo supplier: Commercially available 0.9% Sodium Chloride 100ml infusion bag. This is an authorised product which will be approved stock sourced through the Galway University Hospital pharmacy. The details will be outlined in the IMP handling manual and the product number and batch number will be recorded for the duration of the trial.

9.2 Formulation, packaging and handling

Both placebo (0.9% sodium chloride) and Scopolamine are clear, colourless solutions and infusions are identical once prepared. The pharmacist will dispense the study drug to an unblinded research healthcare professional who will prepare the Scopolamine infusion as per the IMP handling manual (the unblinded healthcare professional will not be involved in assessments or data analysis). Blinding will be maintained as per the process steps and controls outlined in the study specific Investigational Medicinal Product (IMP) Handling Manual.

The Clinical Trials Pharmacy Unit at the HRB-CRFG, will label commercial stock of Scopolamine as per Annex 13 and per approved study instructions. Labels will indicate:

- (i) Use of the treatment in this trial
- (ii) Name of sponsor and CI
- (iii) Trial reference code allowing identification of the trial, site, investigator and participant number
- (iv) The product is 'For Clinical Trial Use Only'

These labels will be added by pharmacy staff on receipt of delivery of the IMP to the HRB-CRFG in accordance with Annex 13 (EU Guidelines to Good Manufacturing Practice, Investigational Medicinal Products).

